PERMANENT PACEMAKER (PPM) IMPLANTATION ⁹⁷	 Implantation of new PPM after the index procedure resulting from new or worsened conduction disturbances Procedure-related: PPM is implanted in subjects with new onset or worsened conduction disturbances occurring post index procedure Not related to procedure: PPM is implanted in subjects with known conduction disturbances that did not advance after the index procedure. Note: See also definitions for arrhythmia and conductance disturbance.
PORCELAIN AORTA	Heavy circumferential calcification of the entire ascending aorta extending to the arch such that aortic cross-clamping is not feasible
PROCEDURE RELATED COMPLICATIONS	Complications associated with any part of the vascular access procedure, associated treatments or necessary secondary interventions that do not necessarily involve the device. This includes morbidity associated with either pre- medication, or anesthesia, or other adjunct to the surgical procedure. Other technical errors including inappropriate subject selection, inappropriate operator techniques, measurements, or judgment that do not involve the device itself are also included.
PROCEDURE- RELATED EVENTS	Events occurring during or as a direct result of the index procedure.
REDUCED LEAFLET MOBILITY/MOTION (RLM) ⁹⁸	 Systolic leaflet excursion/motion is classified as: Grade 0: normal/unrestricted; Grade 1: partially restricted – limited to base; Grade 2: mildly restricted – involving more than the base, but less than 50% of the leaflet along curvilinear dimensions; Grade 3: moderately restricted – involving more than 50% but less than 75% of the leaflet along curvilinear dimensions; Grade 4: largely immobile. Quantitative assessment of leaflet motion is performed with a blood pool inversion volume rendered cine reconstruction throughout the cardiac cycle evaluating the bioprosthetic leaflets.
REPEAT PROCEDURE FOR VALVE- RELATED DYSFUNCTION	Any surgical or percutaneous interventional catheter procedure that repairs, otherwise alters or adjusts, or replaces a previously implanted valve. In addition to surgical re-operations, balloon dilatation, interventional manipulation, repositioning, or retrieval, and other catheter-based interventions for valve-related complications are also considered re-interventions. Cardiac re-interventions will be categorized as repeat TAVR, valvuloplasty, or surgical AVR.

Term	Definition
RESPIRATORY INSUFFICIENCY	Inadequate ventilation or oxygenation
RESPIRATORY FAILURE	The need for ventilatory support for >72 hours associated with an inability to wean from the respirator for any reason.
RIGHT VENTRICULAR INSUFFICIENCY	 Defined as sequelae of right ventricular failure including the following. Significantly decreased right ventricular systolic and/or diastolic function Tricuspid valvular regurgitation secondary to elevated pressure Clinical symptoms to include the following. Hepatic congestion Ascites Anasarca Presence of "hepato-jugular reflux" Edema Severe right ventricular dysfunction or severe pulmonary hypertension is primary or secondary pulmonary hypertension with PA systolic pressures greater than 2/3 of systemic pressure.
SAFETY ANALYSIS SET	This population includes all subjects in the ITT analysis set who have a study device implanted, regardless of the assigned treatment group.
SERIOUS ADVERSE EVENT (SAE) Ref: ISO 14155 Ref: MEDDEV 2.7/3	 Adverse event that: Led to a death Led to serious deterioration in the health of the subject, that either resulted in: a life-threatening illness or injury, or a permanent impairment of a body structure or a body function, or in-patient hospitalization or prolongation of existing hospitalization, or medical or surgical intervention to prevent life- threatening illness Led to fetal distress, fetal death or a congenital abnormality or birth defect Note: Planned hospitalization for a pre-existing condition, or a procedure required by the protocol, without serious deterioration in health, is not considered a serious adverse event.
SERIOUS ADVERSE DEVICE EFFECT (SADE) Ref: ISO 14155 Ref: MEDDEV 2.7/3	Adverse device effect that has resulted in any of the consequences characteristic of a serious adverse event
SOURCE DATA (per ISO 14155)	All information in original records of clinical findings, observations, or other activities in a clinical investigation, necessary for the reconstruction and evaluation of the clinical investigation
SOURCE DOCUMENT (per ISO 14155)	Printed, optical or electronic document containing source data. Examples: hospital records, laboratory notes, device accountability records, photograhic negatives, radiographs, records kept at the investigation center, at the laboratories and at the medico-technical departments involvced in the clinical investigation.
	Note: If thermal paper from a device programmer is to be used for source documentation, signed and dated photocopies or printed portable document format files should be used instead or the strips should be electronically saved.

Term	Definition
STROKE ^{66,67}	Stroke is defined as an acute episode of focal or global neurological dysfunction caused by brain, spinal cord, or retinal vascular injury as a result of hemorrhage or infarction.
	Stroke Classification
	• Ischemic Stroke is defined as an acute episode of focal cerebral, spinal, or retinal dysfunction caused by an infarction of central nervous system tissue.
	• Hemorrhagic Stroke is defined as an acute episode of focal or global cerebral or spinal dysfunction caused by an intraparenchymal, intraventricular, or subarachnoid hemorrhage
	Note: The CEC will adjudicate ischemic versus hemorrhagic stroke.
	Note: A stroke may be classified as undetermined if there is insufficient information to allow categorization as ischemic or hemorrhagic
	Stroke Diagnostic Criteria
	• Rapid onset of a focal or global neurological deficit with at least one of the following: change in level of consciousness, hemiplegia, hemiparesis, numbness or sensory loss affecting one side of the body, dysphasia or aphasia, hemianopia, amaurosis fugax, or other neurological signs or symptoms consistent with stroke
	• Duration of a focal or global neurological deficit ≥24 h; OR <24 h, if available neuroimaging documents a new hemorrhage or infarct; OR the neurological deficit results in death
	• No other readily identifiable nonstroke cause for the clinical presentation (e.g., brain tumor, trauma, infection, hypoglycemia, peripheral lesion,
	pharmacological influences), to be determined by or in conjunction with designated neurologist
	 Confirmation of the diagnosis by at least one of the following. Neurology or neurosurgical specialist
	 Neuroimaging procedure (MRI or CT scan), but stroke may be diagnosed or clinical grounds alone
	Note: Subjects with non-focal global encephalopathy will not be reported as a stroke without unequivocal evidence based upon neuroimaging studies (CT scan or brain MRI).
	Stroke Definitions
	Diagnosis as above, preferably with positive neuroimaging study
	 Non-disabling: Modified Rankin Scale (mRS) score <2 at 90 days OR one that does not result in an increase of at least one mRS category from an individual's pre-stroke baseline
	• Disabling: Modified Rankin Scale score ≥2 at 90 days AND an increase of at least one mRS category from an individual's pre-stroke baseline
	Note: Modified Rankin Scale assessments should be made by a neurology professional or by qualified individuals according to a certification process. Note: Assessment of the mRS score should occur at all scheduled visits in a
	Note: Assessment of the mRS score should occur at all scheduled visits in a study; mRS also should be performed after a stroke and at 90 days after the onset of any stroke.
TAV-IN-TAV DEPLOYMENT	An additional valve prosthesis is implanted within a previously implanted prosthesis because of suboptimal device position and/or function during or after the index procedure.

Term	Definition
TRANSIENT ISCHEMIC ATTACK (TIA)	 Transient episode of focal neurological dysfunction caused by brain, spinal cord, or retinal ischemia, without acute infarction Duration of a focal or global neurological deficit is <24 h
	• Neuroimaging does not demonstrate a new hemorrhage or infarct (if performed)
	Note: The difference between TIA and ischemic stroke is the presence of tissue damage or new sensory-motor deficit persisting >24 hours. By definition, TIA does not produce lasting disability.
UNANTICIPATED ADVERSE DEVICE EFFECT Ref: 21CFR Part 812 (UADE)	Any serious adverse effect on health or safety or any life-threatening problem or death caused by, or associated with a device, if that effect, problem, or death was not previously identified in nature, severity, or degree of incidence in the protocol or application (including a supplementary plan or application), or any other unanticipated serious problem associated with a device that relates to the rights,
(OIDE)	safety, or welfare of subjects.
UNPLANNED USE OF CARDIOPUL- MONARY BYPASS	Unplanned use of cardiopulmonary bypass for hemodynamic support at any time during the TAVR procedure
VALVE EMBOLIZATION	The valve prosthesis moves during or after deployment such that it loses contact with the aortic annulus.
VALVE MALPOSITIONING	Includes valve migration, valve embolization, or ectopic valve deployment
VALVE MIGRATION	After initial correct positioning the valve prosthesis moves upward or downward within the aortic annulus from its initial position, with or without consequences (e.g., regurgitation).
VALVE-RELATED DYSFUNCTION	Mean aortic valve gradient \geq 20 mmHg, EOA \leq 0.9-1.1 cm ² , and/or DVI <0.35 AND/OR moderate or severe prosthetic valve aortic regurgitation (per VARC definition)
VALVE-RELATED SYMPTOMS/CHF REQUIRING HOSPITALIZATION	The need for hospitalization associated with valve-related symptoms or worsening CHF (NYHA Class III or IV) is intended to serve as a basis for calculation of a "days alive outside the hospital" endpoint. Included are heart failure, angina, or syncope due to aortic valve disease requiring intervention or intensified medical management; clinical symptoms of CHF with objective signs including pulmonary edema, hypoperfusion, or documented volume overload AND administration of intravenous diuresis or inotropic therapy, performance of aortic valvuloplasty, institution of mechanical support (intra-aortic balloon pump or ventilation for pulmonary edema), or hemodialysis for volume overload; clear documentation of anginal symptoms AND no clinical evidence that angina was related to coronary artery disease or acute coronary syndrome; documented loss of consciousness not related to seizure or tachyarrhythmia.
VALVE THROMBOSIS	Any thrombus attached to or near an implanted valve that occludes part of the blood flow path, interferes with valve function, or is sufficiently large to warrant treatment. Note that valve-associated thrombus identified at autopsy in a patient whose cause of death was not valve-related or at operation for an unrelated indication should not be reported as valve thrombosis.
VASCULAR ACCESS	Major Vascular Complications
SITE AND ACCESS	• Any aortic dissection, aortic rupture, annulus rupture, left ventricle perforation, or new apical aneurysm/pseudoaneurysm

Term	Definition				
RELATED COMPLICATIONS	• Access site or access-related vascular injury (dissection, stenosis, perforation, rupture, arterio-venous fistula, pseudoaneurysm, hematoma, irreversible nerve injury, compartment syndrome, percutaneous closure device failure*) leading to death, life-threatening or major bleeding**, visceral ischaemia, or neurological impairment				
	• Distal embolization (non-cerebral) from a vascular source requiring surgery or resulting in amputation or irreversible end-organ damage				
	• The use of unplanned endovascular or surgical intervention associated with death, major bleeding, visceral ischaemia or neurological impairment				
	• Any new ipsilateral lower extremity ischemia documented by patient symptoms, physical exam, and/or decreased or absent blood flow on lower extremity angiogram				
	• Surgery for access site-related nerve injury				
	• Permanent access site-related nerve injury				
	Minor Vascular Complications				
	• Access site or access-related vascular injury (dissection, stenosis, perforation, rupture, arterio-venous fistula, pseudoaneurysms, hematomas, percutaneous closure device failure*) not leading to death, life-threatening or major bleeding**, visceral ischaemia or neurological impairment				
	• Distal embolization treated with embolectomy and/or thrombectomy and not resulting in amputation or irreversible end-organ damage				
	• Any unplanned endovascular stenting or unplanned surgical intervention not meeting the criteria for a major vascular complication				
	• Vascular repair or the need for vascular repair (via surgery, ultrasound-guided compression, transcatheter embolization, or stent-graft)				
	*Percutaneous Closure Device Failure				
	Failure of a closure device to achieve hemostasis at the arteriotomy site leading to				
	alternative treatment (other than manual compression or adjunctive endovascular ballooning)				
	Note: Pre-planned surgical access or a planned endovascular approach to vascular closure (e.g., "pre-closure") ^{99,100} should be considered as part of the TAVR				
	procedure and not as a complication, unless untoward clinical consequences are documented (e.g., bleeding complications, limb ischemia, distal embolization, or neurological impairment).				
	 Note: If unplanned percutaneous or surgical intervention does not lead to adverse outcomes this is not considered a major vascular complication. ** Refers to VARC bleeding definitions^{66,67} 				
VENTRICULAR SEPTAL PERFORATION	Angiographic or echocardiographic evidence of a new septal perforation during or after the TAVR procedure				
VESSEL PERFORATION	Unexpected puncture of the vessel with evidence of extravasation into extraluminal surrounding tissue or space requiring treatment using interventional or surgical techniques				
VULNERABLE SUBJECTS (per ISO 14155)	Individuals who are unable to fully understand all aspects of the investigation that are relevant to the decision to participate, or who could be manipulated or unduly influenced as a result of a compromised position, expectation of benefits or fear of retaliatory response				

Term	Definition

Abbreviations: ADE=adverse device effect; AE=adverse event; AR=aortic regurgitation; AVA=aortic valve area; AVR= aortic valve replacement; CEC= Clinical Events Committee; CK= creatine kinase; CT=computed tomography; DVI=Doppler velocity index; ECG=electrocardiogram; EOA=effective orifice area; FEV= forced expiratory volume; GDPR= General Data Protection Regulation; LBBB=left bundle branch block; LV= left ventricle; MI=myocardial infarction; MRI=magnetic resonance imaging; NYHA=New York Heart Association; PPM=permanent pacemaker; RBC=red blood cell; SADE=serious adverse device effect; SAE=serious adverse event; TAV=transcatheter aortic valve; TAVR=transcatheter aortic valve replacement; TEE=transeophageal Doppler echocardiography; TIA=transient ischemic attack; URL=upper reference limit (defined as 99th percentile of normal reference range); VARC=Valve Academic Research Consortium

26. Revision History

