- s: 95% TF and 5% TAx
- t: Includes patients who experienced pericardial tamponade
- u: 90% TF and 10% other
- v: 88% SAPIEN 3 and 12% CoreValve (CoreValve, Evolut R, or Evolut PRO)
- w: 91.2% TF, 7.4% SC, 1.4% TAo
- x: Excludes patients with PPM at baseline
- y: Outcomes at discharge/in-hospital
- z: All bleeding
- Matched cohorts; CoreValve: 93.3% TF, 4.0% SC, 2.2% TAo and 94.7% extreme/high risk, 5.3% intermediate/low risk; Evolut R: 93.2% TF, 4.1% SC, 1.1% TAo and 78.6% extreme/high risk, 21.4% intermediate/low risk
- bb: PPM or implantable defibrillator
- cc: 88% TF and 12% TA/TAo

Abbreviations: AKI=acute kidney injury; LT=life threatening; PPM=permanent pacemaker; PVR=paravalvular regurgitation; SC=subclavian; TA=transapical; TAo=trans-aortic; TAVR=transcatheter aortic valve replacement; TAx=transaxillary; TF=transfemoral/iliofemoral; VARC=Valve Academic Research Consortium; VC=vascular complications

Confidential

Infrequent but significant complications that potentially impact long-term outcomes may limit the utility of TAVR⁵². Suboptimal valve deployment can result in embolization, the need for a second device, or coronary occlusion⁵³. Valve malposition requiring a second TAVR valve at the initial procedure has been associated with increased procedural risk⁵⁴. Placement in a heavily calcified native valve can produce an incomplete seal between the bioprosthetic valve and aortic annulus, resulting in paravalvular regurgitation (PVR), which in turn has been associated with increased mortality⁵⁵⁻⁵⁷. Iterative improvements in TAVR devices and periprocedural technique have reduced but not eliminated PVR^{44,51,58}. The need for permanent pacemaker (PPM) implantation is another limitation of TAVR⁵⁹⁻⁶³.

Newer-generation devices have aimed to address these limitations⁶⁴. The ACURATE TATM Aortic Bioprosthesis (Symetis SA, Ecublens, Switzerland) is a self-expandable nitinol TAVR stent housing a porcine bioprosthesis and placed in a supra-annular position via transapical delivery⁶⁵. The device was designed to allow easy and intuitive implantation (single operator). The ACURATE *neo*TM Aortic Bioprosthesis was subsequently developed for transfemoral (TF) use with the ACURATE *neo*TM TF Delivery System. ACURATE *neo* has a pericardial skirt on the interior and exterior of the stent body which serves to limit PVR⁶⁵.

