6.4. Additional Measurements

This section describes required assessments to be performed in the ACURATE IDE trial.

Additional measurements based on the VARC endpoints and definitions⁶⁶⁻⁶⁸ (see *Note 1* below) will be collected peri- and post-procedure, at discharge or 7 days post-procedure (whichever comes first), 30 days, 6 months, and annually up to 10 years post index procedure, unless otherwise specified below.

- Safety endpoints adjudicated by an independent Clinical Events Committee (CEC; Section 21.1.1):
 - o Mortality: all-cause, cardiovascular, and non-cardiovascular
 - Stroke: disabling and non-disabling
 - Myocardial infarction (MI): periprocedural (≤72 hours post index procedure) and spontaneous (>72 hours post index procedure)
 - Bleeding: life-threatening (or disabling) and major (through 5 years)
 - Acute kidney injury (AKI; ≤7 days post index procedure): based on the AKIN System^{69,70} Stage 3 (including renal replacement therapy) or Stage 2
 - Major vascular complications (through 5 years)
 - Repeat procedure for valve-related dysfunction (surgical or interventional therapy)
 - Hospitalization for valve-related symptoms or worsening congestive heart failure (NYHA class III or IV)
 - New permanent pacemaker implantation resulting from new or worsened conduction disturbances (definitions in Table 25.2-1)
 - New onset of atrial fibrillation or atrial flutter
 - Coronary obstruction: periprocedural (≤72 hours post index procedure)
 - Ventricular septal perforation: periprocedural (≤72 hours post index procedure)
 - Mitral apparatus damage: periprocedural (≤72 hours post index procedure)
 - Cardiac tamponade: periprocedural (≤72 hours post index procedure)
 - Valve migration

- Valve embolization
- Ectopic valve deployment
- Transcatheter aortic valve (TAV)-in-TAV deployment
- Prosthetic aortic valve thrombosis
- Prosthetic aortic valve endocarditis
- Device performance endpoints peri- and post-procedure:
 - Successful vascular access, delivery and deployment of the study valve and successful retrieval of the delivery system
 - o Grade of aortic valve regurgitation: paravalvular, central and combined

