Table 8.3-1: ACURATE IDE Exclusion Criteria

- EC15. Subject has hypertrophic cardiomyopathy.
- EC16. Subject has any therapeutic invasive cardiac or vascular procedure within 30 days prior to the index procedure (except for balloon aortic valvuloplasty, pacemaker implantation, or implantable cardioverter defibrillator implantation, which are allowed).
- EC17. Subject has untreated coronary artery disease, which in the opinion of the treating physician is clinically significant and requires revascularization.
- EC18. Subject has severe left ventricular dysfunction with ejection fraction <20%.
- EC19. Subject is in cardiogenic shock or has hemodynamic instability requiring inotropic support or mechanical support devices.
- EC20. Subject has arterial access that is not acceptable for the study device (test or control) delivery systems as defined in the device (test or control) Directions For Use.
- EC21. Subject has either of the following:
 - Severe vascular disease that would preclude safe access (e.g., aneurysm with thrombus that cannot be crossed safely; marked tortuosity; significant narrowing of the abdominal aorta; severe unfolding of the thoracic aorta; or thick, protruding, ulcerated atheroma in the aortic arch), OR
 - Severe/eccentric calcification of the aortic annulus that would prevent safe implantation of the TAVR prosthesis.
- EC22. Subject has current problems with substance abuse (e.g., alcohol, etc.) that may interfere with the subject's participation in this study.
- EC23. Subject is participating in another investigational drug or device study that has not reached its primary endpoint or subject intends to participate in another investigational device clinical trial within 12 months after index procedure.
- EC24. Subject has untreated conduction system disorder (e.g., Type II second degree atrioventricular block) that in the opinion of the treating physician is clinically significant and requires a pacemaker implantation. Enrollment is permissible after permanent pacemaker implantation.
- EC25. Subject has severe incapacitating dementia.

Abbreviations: CK=creatine kinase; MI=myocardial infarction; TAVR=transcatheter aortic valve replacement

Additional exclusion criteria apply to subjects considered for enrollment in the 4D CT Imaging Substudy as listed below in **Table 8.3-2**.

Table 8.3-2: ACURATE IDE Additional Exclusion Criteria for the 4D CT ImagingSubstudy

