AORTIC DISSECTION	Intimal tear resulting in blood splitting the aortic media and producing a false lumen that can progress in an antegrade or retrograde direction Aortic dissection is further classified using Stanford classification (Types A and B depending on whether ascending or descending aorta involved) or DeBakey classification (Types I, II and III) [see Figure below].

Term	Definition	
	Type A	
AORTIC REGURGITATION (AR)	 The leaking of the aortic valve that causes blood to flow in the reverse direction during ventricular diastole, from the aorta into the left ventricle. The echocardiographic findings in severe aortic regurgitation include the following. An AR color jet dimension >60% of the left ventricular outflow tract diameter (may not be true if the jet is eccentric) The pressure half-time of the regurgitant jet is <250 msec Early termination of the mitral inflow (due to increase in LV pressure due to the AR) Early diastolic flow reversal in the descending aorta. Regurgitant volume >60 mL Regurgitant fraction >55% 	
ARRHYTHMIA	Any variation from the normal rhythm of the heartbeat, including sinus arrhythmia, premature beat, heart block, atrial fibrillation, atrial flutter and tachycardia. Complete heart block, ventricular tachycardia and ventricular fibrillation are considered major arrhythmias. Data should be collected on any new arrhythmia resulting in hemodynamic instability or requiring therapy (therapy includes electrical/medical cardioversion or initiation of a new medication [oral anticoagulation, rhythm or rate controlling therapy]). New onset atrial fibrillation or atrial flutter (AF) is diagnosed as any arrhythmia within hospitalization that has the ECG characteristics of AF and lasts sufficiently long to be recorded on a 12-lead ECG, or at least 30 seconds on a rhythm strip. The therapeutic approach to new-onset AF (spontaneous conversion, electrical or medical cardioversion, initiation of oral anticoagulation, and rate or rhythm control medications) and any clinical consequences should be documented. Note: See also definitions for conductance disturbance and permanent pacemaker.	
BLEEDING ^{66,67}	 Life-threatening or Disabling Bleeding Fatal bleeding (Bleeding Academic Research Consortium [BARC] type 5^{93,94}) Bleeding in a critical organ, such as intracranial, intraspinal, intraocular, or pericardial necessitating pericardiocentesis, or intramuscular with compartment syndrome (BARC type 3b and 3c) 	

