# 5 ADDITIONAL DATA ANALYSES

# 5.1 Adjudicated CEC Event Analysis

For clinical events, the cut-off for events for 30-day endpoints will be 30 days, for 6month endpoints it will be 180 days, for 1-year endpoints it will be 365 days, and for endpoints at 2–10 years it will be 365 days times the number of years. For events at discharge or 7 days post-procedure, the cut-off for events will be the earlier date of discharge or 7 days post-procedure for each subject. The number of evaluable subjects for the CEC event includes subjects who have CEC confirmed events or are in study at least 23, 150, or 335 days (defined as sufficient follow-up in Section 7.3.3) for 30-day, 6month, or 1-year outcome analysis, respectively. For analysis at 2-10 years, the sufficient follow-up is defined as "number of years times 365 minus 45". The number of evaluable subjects for the CEC event at discharge will include all subjects in the specific analysis set.

The Kaplan-Meier rates for all CEC Events will be provided in analyses at 30 days, 6month, and 1-10 years. The survival analysis (including accumulated event curve) for time-to-event endpoint will be provided for selected CEC events, and log-rank test pvalue and wilcoxon test p-value will be provided for comparing two survival curves.

Event to be analysed include the following:

- o Mortality: all-cause, cardiovascular, and non-cardiovascular
- Stroke: disabling and non-disabling
- Myocardial infarction (MI): periprocedural (≤72 hours post index procedure) and spontaneous (>72 hours post index procedure)
- Bleeding: life-threatening (or disabling) and major (through 5 years)
- Acute kidney injury (AKI; ≤7 days post index procedure): based on the AKIN System Stage 3 (including renal replacement therapy) or Stage 2
- Major vascular complications (through 5 years)
- Repeat procedure for valve-related dysfunction (surgical or interventional therapy)
- Hospitalization for valve-related symptoms or worsening congestive heart failure (NYHA class III or IV)
- New permanent pacemaker implantation resulting from new or worsened conduction disturbances
- New onset of atrial fibrillation or atrial flutter
- Coronary obstruction: periprocedural (≤72 hours post index procedure)
- Ventricular septal perforation: periprocedural ( $\leq$ 72 hours post index procedure)
- Mitral apparatus damage: periprocedural ( $\leq$ 72 hours post index procedure)
- Cardiac tamponade: periprocedural (≤72 hours post index procedure)
- Valve migration

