#### 7.3.3 Event Rates

The calculation of binary rates will be the same for any endpoint and time point in regard to the appropriate numbers of days as indicated below in Table 1

Table 1. Days Post-procedure to Event and for Adequate Follow-up for ITT and
Implanted Analysis Sets.

Follow-up Visit	Maximum Days to Event	Days for Adequate Follow-up	
	from	from	
	Randomization/Procedure*	Randomization/Procedure**	
30 Days	30	23	
6 Months	180	150	
12 Months	365	335	
2 Years	730	685	
3 Years	1095	1050	
4 Years	1460	1415	
5 Years	1825	1780	
6 Years	2190	2130	
7 Years	2555	2495	
8 Years	2920	2860	
9 Years	3285	3225	
10 Years	3650	3590	

\* Target date for the follow-up visit.

\*\* Start of the follow-up visit window.

Note: For ITT analysis, the Days are from randomization date. For Implanted, the Days are from procedure date (for non-RCT cohorts, the Days are from procedure date).

Binary event rates (proportions) are calculated on a per subject basis.

Event rates through a follow-up visit are calculated using the following for inclusion in the denominator and numerator:

• Denominator:

Subjects in the specific analysis set count in the denominator with one of the following:

- Subject experiences any CEC adjudicated event ≤ maximum number of days as specified in Table 1, as appropriate or
- $\circ$  date of last follow-up  $\geq$  days for adequate follow-up post-procedure from Table 1, as appropriate:
- Numerator:

Subjects in the specific analysis set count in the numerator if the subject experiences specified event  $\leq$  maximum number of days as specified in Table 1, as appropriate.

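### New-onset AF is defined only in hospital although it is reported to 10 years, and the new-AF and new-pacemaker rates keep subjects who already have the condition in the denominator

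*Protocol*

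**What the plan says.** **Definition.** The arrhythmia entry in Protocol Table 25.2-1 reads: "New onset atrial fibrillation or atrial flutter (AF) is diagnosed as any arrhythmia within hospitalization that has the ECG characteristics of AF". It adds a recording requirement: a 12-lead ECG, or at least 30 seconds on a rhythm strip. It does not say whether the index stay or any stay is meant, and it has no condition on AF history or baseline rhythm. The nearest wording is an instruction on what to record: "Data should be collected on any new arrhythmia resulting in hemodynamic instability or requiring therapy".

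**Reporting window.** Protocol 6.4 lists "New onset of atrial fibrillation or atrial flutter" among the endpoints adjudicated by the Clinical Events Committee (CEC). The list is collected at "30 days, 6 months, and annually up to 10 years post index procedure, unless otherwise specified below". Some entries carry their own limit (72 hours, 7 days or 5 years); new-onset AF does not. Protocol 10.10.5 and 10.10.6 keep new AF and new pacemaker on the list adjudicated in years 6 to 10. SAP 5.1 states: "The Kaplan-Meier rates for all CEC Events will be provided in analyses at 30 days", and continues through 6 months and years 1 to 10.

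**Denominator.** SAP 7.3.3 uses one calculation for all endpoints and time points: "Subjects in the specific analysis set count in the denominator with one of the following". The two routes in are any adjudicated event by the day limit, or adequate follow-up. At discharge, SAP 5.1 counts the whole analysis set.

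**Eligibility.** A pacemaker before enrollment is allowed by EC16 and EC24; the latter says "Enrollment is permissible after permanent pacemaker implantation". AF is not an exclusion for the main cohort. It appears only in the 4D CT substudy criteria (AEC2), and only when the rate cannot be controlled.

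**The concern.** An endpoint reported at 30 days, 1 year and later should be able to occur at those times. Here the definition stops at the hospital door while the reporting continues for a decade. A Kaplan-Meier curve built on it would be nearly flat after discharge, broken only by later admissions, and could be misread as showing that little new AF arises.

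The denominator matters most for pacemakers. Protocol 4.2 presents the valve design as meant to overcome high pacemaker rates, so readers will compare this figure between arms and with published series. Subjects who already have a pacemaker can hardly contribute a new one. Counting them lowers both arms' rates and narrows the absolute difference. It also makes the result hard to set beside studies that count only subjects at risk. Protocol Table 4.1-1 marks one such registry in its notes: "Excludes patients with PPM at baseline".

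**Working it through.** The documents state no planned rate or power for new AF or new pacemaker, so there is no figure to reproduce. The check has two parts.

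**1. Definition against schedule**

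- Protocol Table 10.1-1 requires a 12-lead ECG at baseline, within 1 day, at discharge or 7 days, and at 30 days, 6 months and 1 year. Sections 10.10.1 to 10.10.3 require the last three even when the visit is by telehealth.
- The definition accepts AF only during a hospitalization. If that means the index stay, nothing after discharge counts. If it means any stay, later admissions count but outpatient ECGs do not. On both readings, AF first seen at an outpatient study visit is left out.
- No ECG is scheduled after 1 year, and non-serious adverse events are collected only through 12 months. From year 2, AF can surface only through serious-event and CEC-event reporting.
- The same table ties other definitions to the subject's baseline: kidney injury to baseline creatinine, periprocedural infarction to baseline biomarkers, disabling stroke to the pre-stroke Rankin score. The AF entry has no such link.

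**2. Effect of the denominator**

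Let b be the share of subjects with the condition at baseline and r the rate among those at risk. If subjects with the condition cannot have the event,

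reported rate = r × (1 − b), so r = reported rate / (1 − b).

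A risk difference shrinks by the same factor when b is equal in the two arms. The ratio does not change: r₁(1 − b) / [r₂(1 − b)] = r₁/r₂. A Kaplan-Meier estimate behaves in nearly the same way if censoring is similar in subjects with and without the condition.

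The documents give no value for b; all values below are assumptions.

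- *Pacemaker, r = 12%.* b = 5%: 0.12 × 0.95 = 11.4%. b = 15%: 0.12 × 0.85 = 10.2%. The loss is 0.6 to 1.8 points per arm.
- *Pacemaker, working back from a reported rate.* Two 30-day rates in Table 4.1-1 serve only as figures of realistic size. For 17.4%: 0.174/0.95 = 18.3%, 0.174/0.85 = 20.5%. For 6.5%: 0.065/0.95 = 6.8%, 0.065/0.85 = 7.6% (0.0765).
- *Risk difference of 10 points among those at risk.* b = 5%: 9.5 points. b = 15%: 8.5 points.
- *New AF, r = 10%, known AF not counted as an event.* b = 20%: 0.10 × 0.80 = 8%. b = 40%: 0.10 × 0.60 = 6%.

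**The case against.** An all-subject rate in the ITT or implanted set is well defined and reproducible. Randomization is 1:1, so baseline AF and pacemakers balance in expectation and the relative comparison is hardly touched. Protocol 11.1.4 plans no inference on these additional measurements. SAP 5.6 lists prior AF, flutter and pacemaker as candidate covariates in models of the primary and additional endpoints, so they are not ignored. The pacemaker footnote in Table 4.1-1 marks one registry and does not make the at-risk denominator the protocol's standard. The later-admission reading of the definition still admits some late AF, and the CEC charter, which is not among the documents, may settle details.

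Most of this stands, and it limits the point to descriptive rates and risk differences. It does not remove it. Covariates in a regression do not change a reported rate. SAP 3.4 plans between-arm comparisons of these endpoints, and event rates with credible intervals for other CEC endpoints at the interim, so the absolute figures will be read. Neither reading of hospitalization lets an outpatient ECG count. A rule that exists only in a charter would leave the protocol definition and the SAP reporting plan in conflict.

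**Conclusion.** The point holds in two parts. First, the in-hospital limit contradicts collection, adjudication and Kaplan-Meier reporting to 10 years, and the no-prior-AF criterion is implied but not stated. Second, the common denominator shrinks the absolute new-pacemaker and new-AF rates, and their differences, by (1 − b). For the assumed 5–15% with a pacemaker, that turns 12% into 11.4–10.2%. The size rests wholly on assumed prevalences, on equal b in the two arms, and, for AF, on known AF being kept out of the numerator.

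A reader might go further and infer that subjects with permanent AF would be counted as new cases as soon as a post-procedure ECG shows AF. The documents do not support that. The endpoint's name says new onset, and the sentence before the definition concerns new arrhythmia. Protocol 19.1 keeps underlying disease out of adverse-event reporting unless its severity or frequency increases, and under Protocol 21.1.1 the CEC adjudicates events that investigators report. What is missing is a written criterion. Nor does anything here reach the primary endpoint, its posterior threshold or the sample size of 1500.

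**What to change.** - **Protocol Table 25.2-1:** count AF or flutter that meets the ECG criterion in hospital or on a follow-up ECG, in a subject with no history of AF or flutter and no AF on the baseline ECG. Reconcile the entry with Protocol 6.4, 10.10.5 and 10.10.6. Note that no ECG is scheduled after 1 year, so later events depend on serious-event and CEC-event reporting and detection is less complete than in year 1.
- **SAP 5.1 and 7.3.3:** next to the all-subject rates, add binary and Kaplan-Meier rates of new pacemaker among subjects without a baseline pacemaker, and of new AF among subjects without baseline AF or flutter. State the number at risk in each arm.

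**Cost.** Mostly wording. Cardiac history, the baseline ECG and ECGs to 1 year are already required, and SAP 5.6 already uses AF, flutter and pacemaker history as variables. The at-risk denominators are somewhat smaller and the stated rates higher, and some outpatient AF events will need to be submitted or re-reviewed by the CEC.
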